5.3. Lifestyle Considerations

No lifestyle restrictions are required during the course of this study.

5.4. Screen Failures and Rescreening

Screen failures are defined as participants who consent to participate in the clinical study but following the screening assessments are not subsequently enrolled in the study. A minimal set of screen failure information is required to ensure transparent reporting of screen failure participants to meet the Consolidated Standards of Reporting Trials (CONSORT) publishing requirements and to respond to queries from regulatory authorities. Minimal information includes demography, screen failure details, eligibility criteria, and any serious adverse events (SAEs).

Individuals who do not meet the criteria for participation in this study (screen failure) may be rescreened once at the investigator's discretion following discussion with the Medical Monitor. Such participants will be assigned a new participant number and have all screening assessments repeated.

5.5. Repeat Assessments during the 35 Day Screening Period

Laboratory assessments may be repeated if determined necessary by the investigator, for example: (a) in cases of technical malfunction (e.g., loss of laboratory specimen), (b) in the event of a value close enough to the exclusionary threshold that it may reasonably lie within the degree of variability of the assay; (c) if there is reason to believe the result may be false (e.g. contradicts recent result for the same parameter).

These are repeat assessments and not rescreening events. If the original result was exclusionary and is confirmed by repeat testing, the participant will be excluded.

6. STUDY INTERVENTION

Study intervention is defined as any investigational intervention(s), marketed product(s), placebo, or medical device(s) intended to be administered to a study participant according to the study protocol.

6.1. Study Intervention Administered - Belimumab

ARM Name	Open label arm
Intervention Name	Belimumab
Type	Biologic
Dose Formulation	SC Injection
Unit Dose Strength(s)	200 mg/mL
Dosage Level(s)	Cohort 1 (≥ 50 kg): 200 mg weekly; Cohort 2 (≥ 30 kg - < 50 kg): 200 mg every 10 days; Cohort 3 (< 30 kg): 200 mg every 2 weeks
Route of Administration	SC injection (autoinjector)
Sourcing	Provided centrally by the Sponsor
Packaging and Labelling	Belimumab will be provided in cartons (1 autoinjector/carton). Each carton will be labeled as required per country requirement.
Manufacturer:	Pre-filled syringe: Pre-filled syringe components are procured from Becton Dickinson. Pre-filled syringe is filled with drug product and assembled at GSK, Barnard Castle, UK. Autoinjector: The autoinjector components are manufactured by Scandinavian Health Limited (SHL) and assembled with the pre-filled syringe at GSK, Barnard Castle, UK.
Device	Single use autoinjector

6.1.1. Medical Devices

- The GSK manufactured medical devices (or devices manufactured for GSK by a third party) provided for use in this study are injection devices: a pre-filled syringe contained within an autoinjector device.

- GSK medical device incidents, including those resulting from malfunctions of the device, must be detected, documented, and reported by the investigator throughout the study (see Section 8.9.6).

6.1.1.1. Training for Use of Autoinjectors

Instructions for autoinjector use are provided in the Study Reference Manual. Training will also be provided to sites as described in the Study Reference Manual. Sites will provide training to participants and caregivers and will also provide them with an Instructions for Use. A link for online directions on how to use the autoinjector is provided for reference by site personnel so they are better able to instruct participants/caregivers on correct use.

6.2. Preparation/Handling/Storage/Accountability

1. The investigator or designee must confirm appropriate temperature conditions have been maintained during transit for all study intervention received and any discrepancies are reported and resolved before use of the study intervention.
2. Only participants enrolled in the study by the Interactive Web Response System (IWRS) may receive study intervention and only authorized site staff may supply or administer study intervention. All study interventions must be stored in a secure, environmentally controlled, and monitored (manual or automated) area in accordance with the labeled storage conditions with access limited to the investigator and authorized site staff.
3. The investigator, institution, or the head of the medical institution (where applicable) is responsible for study intervention accountability, reconciliation, and record maintenance (i.e., receipt, reconciliation, and final disposition records).
4. Further guidance and information for the final disposition of unused autoinjectors are provided in the Study Reference Manual.

- Under normal conditions of handling and administration, study intervention is not expected to pose significant safety risks to site staff. Take adequate precautions to avoid direct eye or skin contact and the generation of aerosols or mists. In the case of unintentional occupational exposure notify the monitor, Medical Monitor and/or GSK study contact.
- A Material Safety Data Sheet (MSDS)/equivalent document describing occupational hazards and recommended handling precautions either will be provided to the investigator, where this is required by local laws, or is available upon request from GSK.

6.3. Measures to Minimize Bias: Randomization and Blinding

This is an open-label study with a single treatment arm. The treatment (belimumab) to be taken by a participant will be centrally assigned using an IWRS. The site will contact the IWRS prior to the start of belimumab administration for each participant.

6.4. Subcutaneous Administration of Belimumab

“Self-administration” is defined as administration of study drug either by the study participant or by the participant’s parent/caregiver. All participants less than 12 years old must have the study drug administered by their parent/caregiver. Whether the study drug is administered by the participant for those 12 years and older will be determined by the participant and his/her parents/caregivers.

During screening and on Day 1 (prior to the participant receiving their first dose), qualified study site personnel must review study drug handling and administration techniques with the participant and their caregiver(s). After the first injection of belimumab on Day 1, all subsequent injections should be administered according to the schedule shown in the SOA Section 1.3 ±2 days. Please refer to Section 6.4.2 for guidance regarding missed doses.

If possible, the participant or their caregiver will administer the study agent by SC injection even if administered at the clinic visit. The first three doses will be administered under observation in the clinic. In the post-marketing setting with IV belimumab, delayed onset of symptoms of acute hypersensitivity reactions have been observed. Therefore, at each of the first 2 scheduled administrations of belimumab, participants will be observed by qualified site staff during dosing and will remain under observation at the clinic for 3 hours post-dose. Should symptoms of acute hypersensitivity occur, an extended period of monitoring may be appropriate, based on clinical judgement. Participants and caregivers should be made aware of the potential risk, the signs and symptoms of such reactions, and the importance of immediately seeking medical attention.

Following the 3rd scheduled administration, where allowed by the schedule of activities (see Section 1.3 for definition of which scheduled belimumab injections must be done in clinic), at the discretion of the investigator, participants and caregivers who are adequately trained should administer subsequent doses of belimumab at home following the instructions provided. Participants or their caregivers should not administer the study agent until they receive proper training in subcutaneous injection technique. Participants and caregivers who do not feel adequately trained with self-injection may return to the site for further training. Participants or caregivers who cannot administer the study drug may have subsequent subcutaneous injections delivered by qualified study site personnel, although self-administration should be strongly encouraged. Ideally, the injection site should be rotated between the left or right thigh and the abdomen.

6.4.1. Compliance with Subcutaneous Administration of Belimumab

6.4.1.1. Parts A and B

In Parts A and B, participants and caregivers will be provided with an injection diary (refer to SRM). Dosing compliance must be reviewed with the participant/caregiver at each site visit, the injection diary must be reviewed by study site staff and the entries transcribed to the eCRF. Participants and caregivers are also required to return all used and any malfunctioning autoinjector devices. All unused autoinjectors, including spare devices, must be returned as described in the SRM.

When participants are dosed at the investigative site with belimumab, immediately after the injection, participants or caregivers will complete the injection diary recording the date and time of injection, the injection site and whether or not the entire dose was administered. These injection diary entries will be transcribed into the eCRF by the site staff.

When participants self-administer study treatment(s) at home, immediately after the injection, participants or caregivers will complete the injection diary recording the date and time of injection, the injection site and whether or not the entire dose was administered. Participants must bring their injection diary with them to site visits and compliance with belimumab treatment will be assessed by the site staff through review of the injection diary and transcription of the entries into the eCRF.

A record of the number of belimumab autoinjectors dispensed to and taken by each participant and of unused autoinjectors returned by each participant must be maintained and reconciled with study treatment and compliance records. Used autoinjectors should be placed in a sharps container and returned to the site as described in the SRM. Any returned malfunctioning autoinjectors will be marked to distinguish them from the used autoinjectors (see SRM for details).

6.4.2. Missed Doses

If the participant has not taken the scheduled dose on the due date, the following rules apply:

Weekly dosing – if the scheduled dose has not been administered during the scheduled window the dose should be SKIPPED and dosing should be resumed on the next scheduled date.

10 day dosing – if the scheduled dose has not been administered during the scheduled window it may be administered up to 3 DAYS later. If the dose is not administered within 3 days the dose should be SKIPPED and dosing should be resumed on the next scheduled date.

2 weekly dosing - if the scheduled dose is not administered during the scheduled window it may be administered up to 7 DAYS later. If the dose is not administered within 7 days the dose should be SKIPPED and dosing should be resumed on the next scheduled date.

The participant should not administer 2 doses on the same day and 2 doses should not be administered to make up for a dose missed.

If a participant misses 2 consecutive doses of belimumab or 3 non-consecutive doses of belimumab during Part A, then the Investigator must contact the Medical Monitor to discuss whether the participant should continue in the study (see SRM for details).

If a participant misses 3 or more consecutive doses of belimumab or 4 or more non-consecutive doses of belimumab during Part B, then the Investigator must contact the Medical Monitor to discuss whether the participant should continue in the study. If the participant is allowed to continue they must receive their next dose of belimumab in the

clinic and remain in the clinic for at least 3 hours for observation, as described in Section 6.4 for the initial 2 doses of belimumab.

6.4.2.1. Partial Doses

If a participant has administered a partial dose or was unable to completely self-administer a dose of belimumab due to malfunction of the autoinjector or user error, the participant/caregiver should be instructed to SKIP additional attempts and not re-inject for that period's belimumab dose. Thereafter, the participant should resume self-administering belimumab injections according to their next scheduled day of administration. The participant should not self-administer 2 doses on the same day, even if they believe that they did not receive any medication from the first administration attempt. (See Section 8.9.7 – Medical Device Malfunctions).

6.5. Concomitant Therapy

Any medication or vaccine (including over-the-counter or prescription medicines, vitamins, and/or herbal supplements) that the participant is receiving at the time of screening or receives during the study must be recorded along with:

- reason for use
- dates of administration including start and end dates
- dosage information including dose, route and frequency

The Medical Monitor should be contacted if there are any questions regarding concomitant or prior therapy.

6.5.1. Permitted Concomitant Therapy

Participants must be on a stable SLE treatment regimen for at least 30 days prior to Day 1. Corticosteroids may be added as new medications or their doses adjusted only up to 30 days prior to Day 1.

Once the participant has treatment assigned by the IWRS and receives the first dose of belimumab on Day 1, the investigator may adjust concurrent medications (add, eliminate, change dose level/frequency) as clinically required; however, changes in certain medications (as outlined below) may result in the participant being withdrawn from the study.

6.5.1.1. Anti-malarials

- A new anti-malarial (e.g., hydroxychloroquine, chloroquine, quinacrine) may be started between Day 1 and the 16-week follow-up assessment.
- The dose of an anti-malarial may be reduced or increased as clinically required, between Day 1 and the 16-week follow-up assessment.
- An anti-malarial may be replaced by another anti-malarial due to documented toxicity or lack of availability at any time during the study.

Anti-malarial drugs should be given according to local guidance (see SRM for further details). **NOTE:** The use of anti-malarials for either SLE management or malarial prophylaxis is permitted.

6.5.1.2. Steroids

6.5.1.2.1. Systemic Steroids for SLE-related Disease Activity

- The total dose of systemic steroids may be increased or decreased as clinically indicated from Day 1 through the 16-week post-treatment follow-up assessment (see Section 1.3). Treatment of SLE Flares with Steroids: If a participant has an SLE flare requiring an increase in steroid dose the investigator should consider the guidelines prepared for the ACR, for steroid dose/duration of induction therapy [[Ad Hoc Working Group on Steroid-Sparing Criteria in Lupus, 2004](#)].

6.5.1.2.2. Intra-articular Injections of Corticosteroids

- Participants may receive intraarticular (IA) corticosteroid injections at any time between Day 1 and the 16-week follow-up assessment.

6.5.1.2.3. Steroids for Reasons Other Than SLE Disease Activity

Inhaled and topical steroids are allowed throughout the course of the study.

Steroids may be given for reasons other than SLE disease activity (such as asthma, contact dermatitis) as clinically indicated.

6.5.1.3. Other Immunosuppressive/Immunomodulatory Agents

- Starting any new allowable immunosuppressive/immunomodulatory agent is permitted from Day 1 through the 16-week post-treatment follow-up assessment (See guidance in the SRM).
- The dose of existing immunosuppressive/immunomodulatory agents may be increased or decreased, as clinically required, from Day 1 through the 16-week post-treatment follow-up assessment.

An immunosuppressive/immunomodulatory agent may be replaced with 1 of the agents above due to documented toxicity or lack of availability. New topical immunosuppressive agents (e.g., eye drops, topical creams) are allowed from Day 1 through the 16-week follow-up visit.

6.5.1.4. Nonsteroidal Anti-inflammatory Drugs (NSAIDs)

- NSAIDs may be given within 30 days prior to Day 1 only if given for <1 week. From Day 1 through the 16-week follow-up visit NSAIDs may be given as clinically indicated (even if >1 week). An NSAID may be replaced with another NSAID due to documented toxicity or lack of availability
- Anti-thrombotic doses of aspirin are permitted at any time during the study.

Paracetamol (acetaminophen) is primarily an analgesic and lacks the anti-inflammatory properties of other NSAIDs. The use of paracetamol is recommended when possible to treat non-SLE related conditions, in the absence of a pre-existing hepatic function deficiency.

6.5.2. Prohibited Concomitant Therapy

Participants who start prohibited medications or therapies at any time during the study will be considered a protocol violation. Belimumab will be discontinued and participants will be withdrawn from the study.

The following medications and therapies are prohibited at any time during the study:

- Other investigational agents (biologic or non-biologic). Investigational applies to any drug not approved for sale in the country in which it is being used.
- Participation in a study using an investigational agent or non-drug therapy that may interfere with the conduct of this protocol.
- Anti-TNF or anti-IL-6 therapy (e.g., adalimumab, etanercept, infliximab, certolizumab, tocilizumab, golimumab).
- All biologics (e.g., rituximab, abatacept, interleukin-1 receptor antagonist).
- Intravenous immunoglobulin (IVIG).
- IV cyclophosphamide (oral cyclophosphamide is permitted).
- Plasmapheresis, leukapheresis.
- Any live or live attenuated vaccines. (Participants who require a live or live attenuated vaccine during the study should have belimumab discontinued prior to receiving the vaccine).

Note: Participants' vaccination status should be assessed and current immunization guidelines followed; all necessary vaccinations should be administered no later than 30 days prior to Day 1.

6.6. Dose Modification

No dose modifications of belimumab are allowed. An exception is for a participant whose body weight changes within pre-defined criteria.

The participant must be weighed prior to dosing at each clinic visit and dosing frequency for the next period adjusted according to the criteria below. Site personnel should ensure they provide the participant with sufficient autoinjectors for possible home use prior to the next clinic visit. (See additional details in the SRM).

Part A		Part B and Optional Access Extension Phase		
Dosing cohort	Dosing frequency	Body weight (BW)	Dosing frequency	Note
Cohort 1 (BW ≥ 50 kg at baseline)	Every week	Remains ≥ 50 kg	Every week	
		Decreases to <50 kg	Every 10 days	Revert to every week if BW increases to ≥ 53 kg
Cohort 2 (BW ≥ 30 kg and <50 kg at baseline)	Every 10 days	Remains ≥ 30 kg and <50 kg	Every 10 days	
		Increases to ≥ 53 kg	Every week	Revert to every 10 days if BW decreases to <50 kg
		Decreases to <30 kg	Every 2 weeks	Revert to every 10 days if BW increases to ≥ 33 kg
Cohort 3 ^a (BW <30 kg at baseline)	Every 2 weeks	Remains <30 kg	Every 2 weeks	
		Increases to ≥ 33 kg	Every 10 days	Revert to every 2 weeks if BW decrease to <30 kg

a. If BW drops below 15 kg at any time, suspend dosing and discuss with Medical Monitor to determine if participant should be withdrawn from the study.

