5. For females of childbearing potential: urine pregnancy tests will be provided by sites. Participants will be required to perform a urine pregnancy test every 4 weeks throughout the treatment period (1 onsite and 2 at home). Home urine pregnancy tests will also be provided for the 8-week and 16-week follow-up period. The results of urine pregnancy tests conducted at home will be recorded in the subject diary cards and stored as part of the investigator's source documents. Only positive pregnancy test results will be reported to GSK during the optional access extension phase and will follow the guidance in Section 8.9.5.
6. Participants ≥50 kg at the start of the access extension phase: Study drug to be administered weekly. At home self-administration is encouraged.
7. Participants ≥30 kg - <50 kg at the start of the access extension phase: Study drug to be administered every 10 days. At home self-administration is encouraged.
8. Participants <30 kg at start of the access extension phase: Study drug to be administered every 2 weeks. At home self-administration is encouraged.
9. In the optional access extension phase the dosing frequency may be switched according to any change in body weight. Please refer to Section 6.6 Dose Modification.

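### At entry to the optional access extension, SOA 4 and Section 6.6 give different dosing frequencies to children carrying every-10-day dosing at 50 to <53 kg or every-2-week dosing at 30 to <33 kg

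*Protocol*

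**What the plan says.** SOA 4 (Protocol Section 1.3.4) assigns frequency by weight on entry to the extension, in three footnotes:

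- Footnote 6: "Participants ≥50 kg at the start of the access extension phase: Study drug to be administered weekly".
- Footnote 7: "Participants ≥30 kg - <50 kg at the start of the access extension phase: Study drug to be administered every 10 days".
- Footnote 8: "Participants <30 kg at start of the access extension phase: Study drug to be administered every 2 weeks".

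The row labels show the same plain bands against Day 365 and the 12-weekly visits. Footnote 9, attached to all three dosing rows, adds: "In the optional access extension phase the dosing frequency may be switched according to any change in body weight. Please refer to Section 6.6".

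The right-hand side of the Section 6.6 table is headed "Part B and Optional Access Extension Phase". The section opens with its default: "No dose modifications of belimumab are allowed. An exception is for a participant whose body weight changes within pre-defined criteria". Its criteria are asymmetric. Downward moves occur below 50 kg and below 30 kg. A move up from every 10 days to weekly happens only when weight "increases to ≥ 53 kg", and a move up from every 2 weeks to every 10 days needs at least 33 kg. The same buffer governs return to a former regimen. For a Cohort 1 child who has dropped below 50 kg, the note reads "Revert to every week if BW increases to ≥ 53 kg".

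Sections 4.1 and 6.7.1.5 both send weight-driven changes in this phase to Section 6.6. Neither mentions a fresh allocation by weight at entry. In Part B the corresponding SOA 3 footnotes define the bands by weight at baseline, so that schedule does not re-band anyone.

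**The concern.** Footnotes 6 to 8 look only at weight on the day of entry. Section 6.6 looks at weight and at the frequency the child is already on. A child who has grown past a cut-off but not through the 3 kg buffer can therefore be moved up by one rule and held by the other.

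What is at stake is the dosing instruction, not an endpoint. This phase also offers few ways to notice a wrong frequency. SOA 4 has no PK sampling, Section 6.7.1.5 does not require routine safety laboratory monitoring, and Section 9.4.1 leaves the phase's SAEs out of the in-stream safety review. Sites depend on the written rule, and dispensing for each 12-week interval follows from it.

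**Working it through.** **Step 1. Check the exposure figures.** Section 4.3, Table 1 gives predicted average steady-state concentrations of 88 µg/mL (every 2 weeks) and 123 µg/mL (every 10 days) at 30 kg, and 90 µg/mL (every 10 days) and 129 µg/mL (weekly) at 50 kg. With a fixed 200 mg dose and linear kinetics, average concentration is proportional to 1/interval.

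- At 50 kg: 90 × 10/7 = 128.6, stated as 129.
- At 30 kg: 88 × 14/10 = 123.2, stated as 123.

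The table is consistent with the dosing intervals.

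**Step 2. Apply both rules to the same child.** Section 6.6 is read by the frequency carried into Week 52. If no criterion is met, the current frequency stays, as the section's default requires.

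| Frequency carried in | Weight at Week 52 | SOA 4 | Section 6.6 | Agree? |
|---|---|---|---|---|
| Weekly | 50 to <53 kg | Weekly | Weekly (still at least 50 kg) | Yes |
| Every 10 days | 50 to <53 kg | Weekly | Every 10 days (53 kg not reached) | **No** |
| Every 10 days | 30 to <33 kg | Every 10 days | Every 10 days | Yes |
| Every 2 weeks | 30 to <33 kg | Every 10 days | Every 2 weeks (33 kg not reached) | **No** |
| Every 10 days | ≥53 kg | Weekly | Weekly | Yes |
| Every 10 days | <30 kg | Every 2 weeks | Every 2 weeks | Yes |
| Every 2 weeks | 33 to <50 kg | Every 10 days | Every 10 days | Yes |

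The full grid also shows mismatches for a weekly child under 30 kg and an every-2-week child at 50 kg or more. Weight is recorded at every Part B visit, and the last interval before Week 52 is 8 weeks. Such a child would have to cross two bands between weighings, so I set these cells aside.

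**Step 3. How a child reaches a conflicting row.**

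- A Cohort 2 child who has grown to 51 kg without reaching 53 kg, or a Cohort 3 child who has grown to 31 kg without reaching 33 kg. Here the Section 6.6 answer comes from its default.
- A Cohort 1 child who fell below 50 kg, moved to every 10 days and is back at 51 kg, or a Cohort 2 child who fell below 30 kg, moved to every 2 weeks and is back at 31 kg. Here Section 6.6 states the reversion weight (53 or 33 kg), so explicit text meets explicit text.

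**Step 4. Size.**

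- Concentration ratio: 129/90 = 1.43 (10/7 = 1.43) and 123/88 = 1.40 (14/10 = 1.40).
- Against the 104 µg/mL target at 50 kg: 129/104 − 1 = +24% or 90/104 − 1 = −13%.
- Against the target at 30 kg: 123/104 − 1 = +18% or 88/104 − 1 = −15%.
- Injections per 84-day visit interval: 84/7 = 12 against 84/10 = 8.4, and 84/10 = 8.4 against 84/14 = 6.

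**The case against.** The best defence is that Section 6.6 governs. Footnotes 6 to 8 speak only of the moment of entry. Footnote 9, the note heading SOA 4, Section 4.1 and Section 6.7.1.5 all point weight-driven changes to Section 6.6. Under its default, a child inside the buffer simply keeps the current frequency, which is what a buffer is for, so the lack of a row for 30 to <33 kg or 50 to <53 kg is not much of a gap. This is right for changes after entry. It does not remove the conflict at entry, because footnotes 6 to 8 allocate by weight alone and nothing makes them subject to the frequency already held.

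Three stronger readings are tempting and are not supported:

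- That any child in the two weight bands has conflicting instructions. A Cohort 1 child who stayed weekly, or a Cohort 2 child who passed 53 kg in Part B and is now 51 kg, is weekly under both rules.
- That Section 6.6 replaces 30/50 kg by 33/53 kg. It keeps 30/50 kg for downward moves and for staying in band.
- That the contradiction recurs at every visit as children grow. The row labels carry no time limit, but the footnotes confine the plain bands to entry.

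On size, Section 4.3 treats predicted deviations of up to 25% at the thresholds as acceptable and reports no apparent exposure-response relationship for safety. That stands, and I make no claim that either frequency is unsafe. The Study Reference Manual and the IWRS set-up are not available here and may already settle the matter in practice. That does not mend the protocol text.

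**Conclusion.** The inconsistency is real and narrow. It affects children entering the extension on every-10-day dosing at 50 to <53 kg (weekly under SOA 4, every 10 days under Section 6.6), or on every-2-week dosing at 30 to <33 kg (every 10 days under SOA 4, every 2 weeks under Section 6.6). The difference in drug per unit time is 1.43-fold and 1.40-fold respectively. Although it arises at entry, it can persist. On the reading used here, a child moved up at 51 kg stays weekly while at or above 50 kg, whereas one held back stays on every 10 days until 53 kg.

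The conclusion assumes that Section 6.6 is applied by the frequency carried in, and that the interval ratio in Table 1 holds across each 3 kg band, as linear kinetics imply. The number of children concerned cannot be derived from the documents. They are a subset of roughly 28 enrolled and could be none.

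A reader might infer that the primary PK result is compromised. It is not: the extension has no PK sampling, and both Protocol Section 6.7.1.6 and the SAP (Sections 1 and 3.2) rule out formal analysis of it.

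**What to change.** The sponsor should reconcile SOA 4 footnotes 6 to 8 and the three row labels with Section 6.6, so that one rule applies at extension entry. The wording should say whether the frequency carried from Part B counts at that point. Which rule is right is for the sponsor to decide.

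The sponsor should also confirm that the IWRS and the Study Reference Manual follow the reconciled rule. For any child who has already entered, the weights in source documents and the frequency-change requests in the IWRS (Section 6.7.1.5) should show which rule was applied.

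The cost is a few lines of protocol wording and a check of the system logic. No analysis or table in the SAP changes.
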